8.4 Other Efficacy Variable Analysis

All efficacy endpoints will be summarized descriptively by treatment group. Additional descriptive summaries may be added by treatment group and randomization stratum, separately for all 3 randomization strata.

Figures will be created to display the time course of continuous efficacy endpoints by treatment group.

8.5 Subgroup Analysis

Efficacy variables will be summarized by age (<6 years and ≥ 6 years), gender, the baseline GH-stimulation strata (≤ 5 ng/mL and >5 ng/mL), etiology and extent of GHD (isolated idiopathic vs isolated organic (determined by abnormal MRI) vs multiple pituitary hormone deficiencies) ([Appendix 1](#)).

The Etiology and extent of GHD subgroup definition:

Isolated idiopathic GHD: Subjects without deficiencies of other pituitary axes, and without a history of brain irradiation, and with either a normal MRI assessment or an abnormal MRI that is irrelevant to pituitary gland deficiency based on review of the MRI report text by a medical monitor.

Isolated organic GHD: Subjects without deficiencies of other pituitary axes, and with either a history of brain irradiation, or with an abnormal MRI that is relevant to pituitary hormone deficiency based on review of the MRI report by a medical monitor.

GHD associated with multiple pituitary hormone deficiencies: Subjects with deficiencies of multiple pituitary axes regardless of MRI results.

Abnormal MRI results are considered as relevant to pituitary hormone deficiency if the MRI report states any small or absent pituitary gland or pituitary stalk, or stalk interruption, or ectopic pituitary. The determination of brain irradiation history and the MRI abnormality relevance to pituitary hormone deficiency will be determined by sponsor medical monitor review and will be recorded and captured in the CDISC database.

8.6 Multiplicity Analysis/Procedure

The familywise type-1 error of the study is controlled at 2-sided $\alpha = 0.05$. Non-inferiority for AHV will be tested first, based on the primary analysis (method as described in [Section 8.1](#)). If successful, then the superiority for AHV will be tested next.

9. Safety and Tolerability Analysis

The analysis of safety assessments will include summaries of the following categories of safety and tolerability data collected for each subject and will use the safety analysis set:

Adverse Events

- Adverse Events (AEs), treatment-emergent AEs (TEAEs), and serious adverse events (SAEs)
- AEs leading to withdrawal
- Any deaths

Clinical Laboratory Investigations (Biochemistry, Hematology, Hormone Levels, Glucose Metabolism, Lipid Metabolism, Antibodies)

Vital Signs (blood pressure, heart rate, respiratory rate, body temperature)

Electrocardiograms (ECG)

Physical Examinations

Concomitant Medications

Study Drug Exposure

9.1 Adverse Events

All AEs, TEAEs, and SAEs will be coded using the MedDRA (Version 19.0).

TEAEs are defined as AEs occurring or worsening with an onset at the time of or following the start of treatment with study medication.

If the start date and time of an AE are partially or completely missing, the AE will be assumed to be treatment-emergent if it cannot be definitely shown that the AE did not occur or worsen during the treatment-emergent period (worst case approach). Missing dates and times will not be replaced.

The following are used for guidance for programmers.

- If the start time of an AE is missing, but the start date is complete, an AE will only be excluded from treatment-emergent AEs if the start day is before day of first treatment or the start day is after end day of the treatment-emergent period.
- If the start time and day are missing but the start month is complete, an AE will only be excluded from treatment emergent AEs if the start month is before month of first treatment or the start month is after end month of treatment-emergent period or if the stop date/time is before the start of first treatment.
- If the start day and months are missing but the start year is complete, an AE will only be excluded from treatment-emergent AEs if the start year is before year of first treatment or if the start year is after end year of treatment-emergent period or if the stop date/time is before the start of first treatment.

If the start date is completely missing, an AE will not be excluded from treatment-emergent AEs unless the stop date/time is before the start of first treatment.

All AEs will be summarized in a table whose rows give the number of subjects for each of the following:

- All TEAEs
- SAEs
- Drug-related TEAEs
- TEAEs leading to discontinuation of study drug

Summaries of incidence rates (frequencies and percentages) of individual TEAEs by MedDRA SOC and preferred term will be prepared. Such summaries will be displayed for all TEAEs, TEAEs by maximum intensity, and TEAEs by strongest relationship to study drug.

Each subject will be counted only once within each preferred term. If a subject experiences more than one TEAE within a preferred term only the TEAE with the strongest relationship or the maximum intensity, as appropriate, will be included in the summaries of relationship and intensity.

No inferential statistical tests will be performed.

In the AE data listings, all AEs will be displayed.

9.1.1 Adverse Events Leading to Withdrawal

A summary of incidence rates (frequencies and percentages) of TEAEs leading to withdrawal of study drug, by treatment group, SOC, and preferred term, will be prepared for the Safety Population. No inferential statistical tests will be performed.

A data listing of AEs leading to withdrawal of study drug will also be provided, displaying details of the event(s) captured on the CRF.

9.1.2 Serious Adverse Events

A summary of incidence rates (frequencies and percentages) of SAEs by treatment group, SOC, and preferred term will be prepared for the Safety Population. No inferential statistical tests will be performed.

A data listing of SAEs will also be provided, displaying details of the event(s) captured on the CRF.

9.2 Clinical Laboratory Evaluations

Descriptive summaries of actual (absolute) values and changes from baseline values if applicable will be presented for the following by treatment and visit in both original and standard units for the Safety Population using central laboratories data:

- Biochemistry: sodium, potassium, calcium, phosphate, chloride, total bilirubin, alkaline phosphatase, lactate dehydrogenase (LDH), aspartate aminotransferase (AST), alanine aminotransferase (ALT), gamma glutamyl transferase (GGT), albumin, total protein, creatinine, urea nitrogen, uric acid, serum iron and transferrin
- Hematology: hemoglobin, leukocytes, differential blood count of leukocytes, platelet count
- Hormone Levels: thyroid status (TSH, fT4, and fT3 levels) and morning cortisol
- Glucose Metabolism: HbA1c, and fasting insulin and glucose, HbA1c.
- Lipid Metabolism: Total cholesterol, triglycerides, HDL and LDL

Laboratory values will be displayed in the data listings and those that are outside the normal range will be flagged, along with corresponding normal ranges. Any out-of-range values that are identified by the investigator as being clinically significant will be presented in a data listing. For each laboratory parameter, if applicable, shifts in assessments of abnormality from baseline to each post-baseline visit will be presented (shift tables) for data from central laboratories.

Data listings of laboratory will also be provided, displaying details of each laboratory test captured on the CRF for central and local laboratories separately.

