10.3. Assessments

10.3.1 Safety and Efficacy

Safety and efficacy assessments will be performed throughout the trial. All samples obtained after Informed Consent will be shipped to a selected central laboratory for analysis. Safety samples may be analyzed locally in case of emergency or if logistics or other unforeseen events do not permit a central analysis. During visits where study drug administration is planned at the site, these assessments will be performed prior to such administration (predose). While fasting is recommended for all visits, fasting is required at Visits 1, 4, and 6. The following procedures will be performed during V1 through V6 unless otherwise indicated:

- 1) Physical examination and vital sign measurement (blood pressure, heart rate, body temperature, respiratory rate) (subjects should rest for at least 5 minutes before vital sign assessment)

- 2) Review of concomitant medication
- 3) Review of Subject Diary by investigator (V2-V6)
- 4) Evaluation of AEs and local tolerability
- 5) Safety assessments:
 - Hormone levels {TSH, fT4, fT3, and morning cortisol; V1 (fasting), V3, V4 (fasting) and V6 (fasting)}
 - Routine safety biochemistry parameters (sodium, potassium, calcium, phosphate, chloride, total bilirubin, alkaline phosphatase, LDH, AST, ALT, GGT, albumin, total protein, creatinine, urea-nitrogen, uric acid, serum iron and transferrin)
 - Hematology parameters (hemoglobin, leukocytes, differential blood count of leukocytes, platelet count; blood smears will be performed locally for back-up analysis, if needed)
 - Parameters of glucose metabolism: fasting glucose (when required), insulin, and HbA1c (glucose metabolism parameters can be assessed locally at any time if there is suspicion of impaired glucose tolerance, which may include an OGTT)
 - Parameters of lipid metabolism (cholesterol, LDL and HDL, and triglycerides)
- 6) Immunogenicity assessment: anti-hGH and anti-PEG antibodies (Cohort 2: anti-PEG antibodies only at Screening and V1 predose, in support of trial specific assay cut-point determination); a subject with observed anti-hGH binding antibodies post dosing (V3-V5) at or close to the C_{max} for TransCon hGH may be brought back for a repeat sample to assess for neutralizing antibodies at a time point deemed appropriate to exclude assay interference. Anti-PEG antibodies will only be analyzed at the end of the individual treatment period once all samples from an individual subject are available.

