13.4.5 Safety Analyses

The safety endpoints of the trial are listed in [Section 13.1.3](#). The assessment of safety will be based mainly on the frequency of AEs, frequency of antibody development, serum IGF-1 levels and the number of laboratory values that fall outside of laboratory specified reference ranges. Other safety data (eg, vital signs, special tests, etc.) will be considered as appropriate.

Safety endpoints will be summarized using descriptive statistics. AEs will be listed by cohort and subject number. AEs will be tabulated by cohort, body system, severity and the relationship to the study drug. Changes in laboratory variables will be displayed on shift tables and through the tabulation of summary statistics for each variable. Other information collected (eg, severity or relatedness to the study drug) will be listed as appropriate.

If appropriate, laboratory and/or ECG data will be summarized by presenting shift tables using extended normal ranges (baseline to most extreme post baseline value), by presenting summary statistics of raw data (means, medians, standard deviations, ranges) and change from baseline values and by flagging of notable values in data listings.

Data from other tests (eg, blood pressure or vital signs) will be listed, notable values will be flagged, and any other information collected will be listed as appropriate. Summary statistics will be given where appropriate.

In addition, the number and percentage of subjects developing anti-hGH binding and neutralizing antibodies and developing or increasing anti-PEG antibodies (TransCon hGH cohort only) will be summarized by cohort.

Local tolerability will be summarized based on the investigator's (and subject's/subject's parents/legal guardians) assessment of pain, erythema, bruising, itching, and swelling.

The safety analysis will be based upon the SAS subset.

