14.3.3 Laboratory Data Summary Tables

Table 14.3.3.1.1	SAFETY	Summary of Central Laboratory Data - Hematology by Visit (Conventional Units)
Table 14.3.3.1.2	SAFETY	Summary of Central Laboratory Data - Hematology by Visit (SI Units)
Table 14.3.3.2	SAFETY	Central Laboratory Data - Hematology: Assessments (SI Units) by Visit
Table 14.3.3.3	SAFETY	Central Laboratory Data - Hematology: Shift in Assessments Compared to Baseline (SI Units)
Table 14.3.3.4.1	SAFETY	Summary of Central Laboratory Data - Biochemistry by Visit (Conventional Units)
Table 14.3.3.4.2	SAFETY	Summary of Central Laboratory Data - Biochemistry by Visit (SI Units)
Table 14.3.3.5	SAFETY	Central Laboratory Data - Biochemistry: Assessments by (SI Units) Visit
Table 14.3.3.6	SAFETY	Central Laboratory Data - Biochemistry: Shift in Assessments Compared to Baseline (SI Units)
Table 14.3.3.7.1	SAFETY	Summary of Central Laboratory Data – Glucose Metabolism by Visit (Conventional Units)
Table 14.3.3.7.2	SAFETY	Summary of Central Laboratory Data - Glucose Metabolism by Visit (SI Units)
Table 14.3.3.8	SAFETY	Central Laboratory Data - Glucose Metabolism: Assessments (SI Units) by Visit
Table 14.3.3.9	SAFETY	Central Laboratory Data - Glucose Metabolism: Shift in Assessments Compared to Baseline (SI Units)
Table 14.3.3.10.1	SAFETY	Summary of Central Laboratory Data – Lipid Metabolism by Visit (Conventional Units)
Table 14.3.3.10.2	SAFETY	Summary of Central Laboratory Data - Lipid Metabolism by Visit (SI Units)
Table 14.3.3.11	SAFETY	Central Laboratory Data - Lipid Metabolism: Assessments (SI Units) by Visit
Table 14.3.3.12	SAFETY	Central Laboratory Data - Lipid Metabolism: Shift in Assessments Compared to Baseline (SI Units)
Table 14.3.3.13.1	SAFETY	Summary of Central Laboratory Data – Hormone Status by Visit (Conventional Units)
Table 14.3.3.13.2	SAFETY	Summary of Central Laboratory Data - Hormone Status by Visit (SI Units)
Table 14.3.3.14	SAFETY	Central Laboratory Data - Hormone Status: Assessments (SI Units) by Visit
Table 14.3.3.15	SAFETY	Central Laboratory Data - Hormone Status: Shift in Assessments Compared to Baseline (SI Units)
Table 14.3.3.16.1	SAFETY	Summary of Antibodies
Table 14.3.3.16.2	SAFETY	Summary of Antibodies by visit

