16.2.8 Laboratory Values (by Subject)

- Data Listing 16.2.8.1.1 Hematology Central Laboratory Evaluations
- Data Listing 16.2.8.1.2 Hematology Local Laboratory Evaluations
- Data Listing 16.2.8.2.1 Biochemistry Central Laboratory Evaluations
- Data Listing 16.2.8.2.2 Biochemistry Local Laboratory Evaluations
- Data Listing 16.2.8.3.1 Glucose Metabolism Central Laboratory Evaluations
- Data Listing 16.2.8.3.2 Glucose Metabolism Local Laboratory Evaluations
- Data Listing 16.2.8.4.1 Lipid Metabolism Central Laboratory Evaluations
- Data Listing 16.2.8.4.2 Lipid Metabolism Local Laboratory Evaluations
- Data Listing 16.2.8.5 Hormone Status Local Laboratory Evaluations
- Data Listing 16.2.8.6.1 Antibodies Evaluation
- Data Listing 16.2.8.6.2 Antibodies Status Over the Whole Study
- Data Listing 16.2.8.7 Oral Glucose Tolerance Test (Local Laboratory)

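### Laboratory tables use central data only, so locally run abnormal values, including OGTTs, are listed but not counted by arm

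*SAP*

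**What the plan says.** SAP 9.2 gives descriptive laboratory summaries "by treatment and visit in both original and standard units for the Safety Population using central laboratories data". For abnormality, "shifts in assessments of abnormality from baseline to each post-baseline visit will be presented (shift tables) for data from central laboratories". The list of planned tables follows suit: every hematology, biochemistry, glucose, lipid and hormone table (14.3.3.1.1 to 14.3.3.15) is titled as central laboratory data.

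Protocol 10.3.1 ships post-consent samples to a central laboratory by default and then allows two exceptions. The first is general: "Safety samples may be analyzed locally in case of emergency or if logistics or other unforeseen events do not permit a central analysis". The second is specific to glucose: "glucose metabolism parameters can be assessed locally at any time if there is suspicion of impaired glucose tolerance, which may include an OGTT". The glucose exception also appears in protocol 10.1.1 and 10.1.2.

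Local results are kept. SAP 9.2 lists them separately from central results, and SAP 16.2.8 names the listings, among them 16.2.8.3.2 for local glucose metabolism and 16.2.8.7 for the OGTT. The OGTT is not among the glucose parameters summarized in SAP 9.2 and has no table.

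Protocol 9.6 names levels of HbA1c, fasting glucose and 2-hour OGTT glucose as guides to dose decisions. Protocol 13.4.5 names the number of laboratory values outside reference ranges as one of the main bases of the safety assessment and does not distinguish central from local sources.

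**The concern.** Glucose metabolism is a named safety endpoint (protocol 13.1.3, SAP 2.2.2), and hyperglycemia is a listed risk (protocol 11.1.1). Two of the permitted reasons for local testing, suspected glucose intolerance and emergency, arise when something may be wrong. If those results stay out of every laboratory table, the missing values are plausibly more often abnormal than the tabulated ones, and the by-arm count of abnormal values is incomplete.

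The OGTT is the clearest case. It is one of three glucose criteria in protocol 9.6, yet no output compares it between arms. A listing lets a reader follow one child but gives no frequency by treatment.

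**Working it through.** The plan states no figure on this point, so there is none to reproduce. The check traces where each kind of result goes, then gives a sense of scale.

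**Step 1. Routing of results** (protocol 10.3.1 and 11.1.3; SAP 6.1.3, 9.1, 9.2, 14.3.3 and 16.2.8)

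| Result | Laboratory tables | Other output |
|---|---|---|
| Scheduled glucose, insulin, HbA1c (V1 to V6), analyzed centrally | Yes | Central listing |
| Unscheduled sample, analyzed centrally | Yes, in shift tables (SAP 6.1.3 includes all data points) | Central listing |
| Glucose, insulin or HbA1c run locally | None | Listing 16.2.8.3.2; TEAE tables if the AE definition is met |
| OGTT | None | Listing 16.2.8.7; TEAE tables if the AE definition is met |
| Other safety sample run locally | None | Local listings; TEAE tables if the AE definition is met |

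The all-data-points rule in SAP 6.1.3 helps with the second row. It does not help with the last three, because SAP 9.2 limits the shift tables to central data. Under protocol 11.1.3 an abnormal laboratory value is an AE only if it causes signs or symptoms, is considered clinically significant or requires therapy. Meeting a protocol 9.6 level is not in itself one of those conditions. A local value can therefore meet a 9.6 level and be counted in no table.

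**Step 2. Could a scheduled central sample pick up the same episode?** The target days in SAP Table 3 are 1, 29, 88, 179, 270 and 365. The gaps are 29 − 1 = 28, 88 − 29 = 59, 179 − 88 = 91, 270 − 179 = 91 and 365 − 270 = 95 days. For a child with no prior evidence of glucose intolerance who reaches a 9.6 level, protocol 9.6 asks for repeat fasting glucose and HbA1c within 2 to 4 weeks, that is 14 to 28 days. From Week 5 onward the shortest gap is 59 days, so a repeat prompted by a scheduled visit normally falls before the next one. If the repeat is analyzed centrally, it enters the shift tables. If it is run locally, it is only listed. HbA1c is scheduled centrally at every visit. Fasting is required on treatment only at Weeks 26 and 52 and is recommended at the other visits.

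**Step 3. Weight of one child.** The planned arms are about 100 (TransCon hGH) and 50 (Genotropin). If *k* children in an arm of size *n* have an abnormality seen only locally, the tabulated incidence is too low by *k*/*n*.

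- One child: 1/100 = 1 percentage point; 1/50 = 2 points.
- Assumed range of 1 to 5 children in an arm: 1 to 5 points for TransCon hGH; 2 to 10 points for Genotropin.

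The range for *k* is an assumption. The difference between arms shifts by *k*_T/100 − *k*_G/50, so equal rates of local-only abnormality (for example 2 and 1 children) cancel in the difference but still lower both incidences.

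**The case against.** Four points on the other side carry weight.

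- **Local testing is the exception.** The protocol says may and can, and logistics is one of the reasons. A reader might infer that suspected cases are sent to local laboratories, or that a local value always signals a suspected problem. The documents support neither. That local values are more often abnormal is a reasonable inference, not a documented fact.
- **Safety tables are wider than laboratory tables.** A reader might infer that local abnormalities never reach a safety table. They can: symptomatic, clinically significant or treated abnormalities are AEs and enter the TEAE tables, and glucose-lowering treatment would enter the concomitant medication table. What remains uncounted is the local abnormality that meets none of these conditions.
- **The protocol left room.** Protocol 13.4.5 mentions shifts from "baseline to most extreme post baseline value", and the SAP plans shifts only to each visit. That sentence opens with a qualifier making it conditional on being appropriate, and protocol 13 makes the final SAP the analysis of record. Visit-wise shifts are a permitted choice, not a breach.
- **Central-only tables have a purpose.** Assays and reference ranges differ between laboratories, and scheduled central testing follows the same visits in both arms. In an open-label trial, for-cause local testing may be ordered more readily in one arm, so pooling it into the main shift tables could itself distort the comparison.

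These points justify leaving the existing tables alone. They do not supply the missing count: no planned output gives, by arm, the children who met a 9.6 glucose level on any test, or any OGTT result.

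**Conclusion.** The gap is real but limited. Laboratory tables omit all local values and all OGTT results, so the by-arm frequency of abnormal glucose values can be understated by about 1 point (TransCon hGH) or 2 points (Genotropin) per child whose abnormality is seen only locally. This assumes the planned arm sizes of about 100 and 50. The number of such children is unknown and could be zero.

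Scheduled central HbA1c, unscheduled central samples and the AE tables each reduce the effect. The documents do not support saying that an affected child would look normal in every table, or that the tables are biased by a known amount. No efficacy result or type I error is involved. The addition is worth making because protocol 13.4.5 relies on counts of out-of-range values without limiting their source, and because a criterion used in protocol 9.6 has no summary.

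**What to change.** Keep the central-only means and visit-wise shift tables. Add one supplementary by-arm table to SAP 9.2 and to the 14.3.3 list, with these contents:

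1. Children with any post-baseline central or local value meeting the existing protocol 9.6 levels, by criterion (HbA1c, fasting glucose, 2-hour OGTT) and overall, each child counted once per row.
2. Children with any local out-of-range safety value, classified against that laboratory's own range.
3. Central-only and central-plus-local counts side by side for item 1, with the number of children tested locally in each arm.

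The footnote should say that local tests are for-cause and unblinded, so ascertainment may differ by arm, and that between-laboratory assay variation affects the fixed 9.6 levels. Using each laboratory's own range addresses this for item 2 only. The number tested locally lets a reader judge the ascertainment problem.

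The cost is a paragraph of SAP text and one table. The planned local listings indicate that the data are already captured.
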